Physical Activity Intervention for Adolescent Girls

Clinical Trials NCT04190225

Study Protocol and Statistical Analysis Plan

September 4, 2024

Trial Design and Setting

Chicas Fuertes is a parallel group randomized trial. Adolescent Latinas (N=200) living in San Diego County are randomized 1:1 to receive either the mobile technology-based MVPA intervention or only a wearable tracker (control group); analyses will test the superiority of the intervention over the control condition in increasing MVPA. Participants assigned to the intervention first receive a face-to-face counseling session to learn behavior change techniques. These sessions are conducted in a number of settings such as local parks, classrooms, and community-based organizations. They then receive a Fitbit and access to a tailored intervention website to reinforce goal setting and self-monitoring. Participants also are connected to a study Instagram account, and receive regular text messages automatically generated by data from wearable trackers that update participants on goal progress and encourage adaptive goal setting. Activity is measured at baseline and follow-up via accelerometers and the 7-Day Physical Activity Recall (PAR) Interview, and throughout the study using Fitbits. Measures are taken again at 12 months to evaluate maintenance of activity gains. The sponsor and funder, the National Institutes of Health, played no part in study design. They have no role in the collection, management, analysis, and interpretation of data. They played no part in writing of the protocol and the decision to submit the protocol for publication. The study protocol uses SPIRIT reporting guidelines ¹.

Participants

Eligibility criteria

Potential participants must self-identify as Latina, be 13-18 years old, read, write, and speak English, and be underactive, defined as regularly participating in MVPA for less than 150 minutes per week. Participants must also have regular (≥ 2 times/week) access to the Internet and to a cell phone that can receive and send text messages. Interested participants who do not have access to a smartphone are provided equipment to sync the Fitbit with a computer and

use the Fitbit website dashboard rather than the smartphone app.

Intervention

Intervention description

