To increase enrollment and retention in the study, Fitbit devices and incentives in the form of cash payments and gift cards are provided to all participants. At baseline, each participant receives a Fitbit Inspire HR activity tracker to use throughout the study and keep after study participation is completed. Incentive payments of \$25, \$50, and \$50 are provided at the baseline, 6-, and 12-month follow-up measurement visits, respectively. Additionally, participants receive an additional \$25 bonus if they complete all measures at the 6- and 12-month visits. Lastly, while in-person research was suspended at UC San Diego (March 2020 – August 2020) and is limited (August 2020 – present) to mitigate the spread of COVID-19, remote follow-up measurement visits are offered to participants unable to return in-person. This includes completing self-report surveys online.

Outcomes

Primary outcome

The primary outcome is change in weekly minutes of MVPA from baseline to six months measured by the ActiGraph GT3X+ accelerometer. The ActiGraph GT3X+ is a hip-worn triaxial accelerometer which measures movement and intensity of activity and has been validated against heart rate telemetry ⁹ and total energy expenditure ¹⁰, including in children.¹¹ Participants wear the ActiGraph for ≥ 12 hrs/day ≥ 7 days at baseline and follow-up. Participants receive regular text messages to remind them to wear the ActiGraph. Valid wear time is considered ≥ 3000 minutes on ≥ 4 days. Data is processed using Freedson's age-specific cut points for children to identify activity at various intensities.¹² We will evaluate total minutes of MVPA and total time in 10+ minute bouts.

As an additional measure of MVPA change, at baseline and follow-up participants also engage in the 7-Day PAR interview. The 7-Day PAR is a semi-structured interview that assesses frequency, duration and intensity of MVPA. It has consistently demonstrated acceptable reliability, internal consistency, and congruent validity with objective MVPA measures ^{13,14} and sensitivity to changes over time.^{15,16} It has been validated in children as young as 11.¹⁷ Administering the PAR requires annual certification. To ensure fidelity of PAR measures, a random sample of 5% of PAR interviews are recorded and assessed for fidelity by an external consultant.

Secondary outcomes and covariates

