One week after the orientation visit, participants attend an in-person baseline visit. Due to COVID-19 restrictions, in-person visits are conducted outdoors at parks close to the participant's home. Participants return the accelerometer, which is assessed for sufficient wear time (≥ 3000 minutes on ≥ 4 days). After performing a short walk to demonstrate activity of a moderate intensity level, participants complete the 7-Day PAR interview ^{13,17}. Once all baseline measures are completed, including all online psychosocial questionnaires, participants are randomized to either the multi-media MVPA intervention, or to a control group receiving only a Fitbit.

Follow-up visits

The primary outcome is change in MVPA from baseline to six months, with maintenance of activity at 12 months serving as a secondary outcome. Follow-up visits are conducted remotely via Zoom software. Prior to the six- and 12-month visits, participants are mailed the accelerometer for one week of wear, similar to baseline. Accelerometers are mailed back and checked for wear time, after which participants complete the PAR interview over Zoom, and fill in online psychosocial questionnaires. Participants also complete a contamination measure at six and 12 months to assess amount and type of contact with participants in other conditions. At 12 months, a consumer satisfaction measure is completed by those in the Intervention arm to assess the acceptability of the Chicas Fuertes MVPA intervention, and a subset of participants engage in a one-on-one interview to give additional feedback about the program. Participants receive \$50 for completing the baseline, 6- and 12-month measures, \$25 for correctly wearing

and returning the accelerometer, and \$25 for completing all other measures. Participants receive an additional \$25 bonus at month 12 if they complete all measures at all visits.

Recruitment

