As min/week of MVPA was skewed and attempts to transform towards normality were unsuccessful, a series of quantile regression models with bootstrapped standard errors (10,000 bootstrapped samples) were used to regress median min/week MVPA on baseline values, group, and covariates. Models were run separately for self-reported MVPA (via the PAR) and objectively measured (using accelerometry). Models for the latter further adjusted for accelerometer wear time. As a small proportion of study participants were yoked together during the randomization process (siblings, cousins, or close friends who enrolled together), we adjusted for clustering by yoked group in each of our models (to ensure standard errors were adjusting for non-independence of outcomes within-cluster). All other covariates were balanced at baseline and tested for significance in the model before being dropped.

To understand the group differences in minutes of PA as collected via the Fitbit, we examined data from the weeks corresponding to measurement of PA via the PAR and accelerometer. Using a longitudinal mixed effects model with subject-specific intercepts, we examined group differences adjusting for clustering by yoked pair.

All analyses were carried out in R, with significance level set at .05 a priori.

1. Chan A-W, Tetzlaff JM, Gøtzsche PC, et al. SPIRIT 2013 explanation and elaboration: guidance for protocols of clinical trials. *BMJ : British Medical Journal*. 2013;346:e7586. doi:10.1136/bmj.e7586

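### Does evaluating both total MVPA minutes and time in 10+ minute bouts leave the primary test undecided?

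*Combined protocol and SAP*

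**What the plan says.** The Primary outcome section of the combined protocol and SAP gives a single definition: "The primary outcome is change in weekly minutes of MVPA from baseline to six months measured by the ActiGraph GT3X+ accelerometer". After describing wear time and cut points, the same paragraph adds: "We will evaluate total minutes of MVPA and total time in 10+ minute bouts". The next paragraph places the recall interview below the accelerometer: "As an additional measure of MVPA change, at baseline and follow-up participants also engage in the 7-Day PAR interview".

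Three other places refer to the outcome:

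- **Trial Design and Setting:** "analyses will test the superiority of the intervention over the control condition in increasing MVPA".
- **Follow-up visits**, on the time points: "The primary outcome is change in MVPA from baseline to six months, with maintenance of activity at 12 months serving as a secondary outcome".
- **Statistical Analysis:** median regression models "were used to regress median min/week MVPA on baseline values, group, and covariates", run separately for the recall interview and for accelerometry, and later "All analyses were carried out in R, with significance level set at .05 a priori".

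Bouts are mentioned only in the Primary outcome section. They are not listed under Secondary outcomes and covariates, and the Statistical Analysis section does not refer to them.

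**The concern.** The sentence on bouts stands under the primary heading and joins two quantities with no order between them. Time in bouts is also expressed in minutes per week, so the general phrases used elsewhere could be stretched to cover either quantity. The plan ranks the recall interview and the 12-month time point but not these two, and it gives no testing order or multiplicity rule.

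The superiority claim is at stake. If total minutes and bouted minutes disagreed, and the authors felt free to present whichever was favourable as the primary result, the trial would have had two chances at a 5% test.

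The Statistical Analysis section also chose its model after looking at the data ("As min/week of MVPA was skewed and attempts to transform towards normality were unsuccessful"). That may raise the further question of whether the form of the outcome was settled late as well.

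**Working it through.** **Step 1: is there a second primary test in the text?**

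| Place | Wording in substance | Fits total minutes | Fits bouts only |
|---|---|---|---|
| Primary outcome, definition | weekly ActiGraph MVPA minutes, singular outcome | yes, as written | only with an added restriction |
| Primary outcome, later sentence | both quantities evaluated | yes | yes |
| Trial Design and Setting | increasing MVPA | yes | only with an added restriction |
| Follow-up visits | change in MVPA | yes | only with an added restriction |
| Statistical Analysis | MVPA minutes per week, separate models by instrument | yes | only with an added restriction |

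Time in bouts of 10 minutes or more is a subset of total MVPA time. A subset needs a qualifier, and no definition or model statement carries one. The only sentence that mentions bouts follows the account of wear time and cut points, where it reads as a list of what is derived from the device. The text therefore supports one primary accelerometer analysis, on total minutes.

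**Step 2: error rate on that reading.** One test at .05 gives a type I error of 5%.

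**Step 3: error rate if either quantity could count as success.** This is hypothetical.

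Inputs:
- .05 for each test, from Statistical Analysis. Two-sided is assumed, because the sidedness is not stated.
- Critical value c = 1.96.
- Bivariate normal test statistics with correlation r. This is an assumption; the documents give no r, and the planned analysis is a bootstrapped median regression.

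Independent tests: 1 − (1 − .05)² = 1 − .9025 = .0975.

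Correlated tests, with Φ₂ the bivariate normal distribution function:
- Two-sided: 1 − [Φ₂(c, c) − Φ₂(−c, c) − Φ₂(c, −c) + Φ₂(−c, −c)]
- In the intervention's favour only: 1 − Φ₂(c, c)

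| r | Two-sided | Favouring intervention |
|---|---|---|
| 0 | .0975 | .0494 |
| 0.5 | .0907 | .0454 |
| 0.7 | .0835 | .0417 |
| 0.8 | .0781 | .0390 |
| 0.9 | .0704 | .0352 |
| 0.95 | .0646 | .0323 |

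The single-test references are .05 and .025. Because bouted time is part of total time, independence is implausible.

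**Step 4: what formal multiplicity control would cost.** If both quantities were treated as primary and each was first tested at .025, a test with 80% power at .05 would have noncentrality 1.960 + 0.842 = 2.802. The critical value at .025 is 2.241, so power is Φ(2.802 − 2.241) = Φ(0.561) ≈ .71. Power at that level falls from 80% to 71%. The 80% is illustrative, since the document states no power.

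**The case for a change.** The strongest case for a change is that this reading is inference. No sentence says that total minutes decide and bouts support. The protocol labels other measures as additional or secondary, so its silence here is noticeable, and the planned evaluation of bouts has no described model. A short statement would settle the point at almost no cost and would bear on the trial's central claim. The arithmetic in Step 3 is correct for the rule it assumes.

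What stands is narrow: the role of bouts is not written down. The rest does not carry over to the primary test. The inflated error rates depend on an either-quantity success rule that appears nowhere. The absence of a bouts model fits a descriptive role at least as well as a hidden second test. The skewness remark concerns the choice of regression model. It says nothing about when total minutes or bouts was selected, and belongs to a separate discussion of data-driven model choice. Splitting the significance level would give bouts a primary status that the document does not give them, and would lose power over a label.

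**Conclusion.** No change to the plan follows. This is a missing detail that an analyst would fill in the obvious way: test total ActiGraph MVPA minutes per week at six months at .05, and report time in 10+ minute bouts as supporting information. The conclusion is then sound and the type I error is 5%. A report that put bouts forward as the deciding result would depart from the stated primary outcome, and a reader holding the protocol could see that.

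The figures of about 6.5% to 9.1% two-sided (3.2% to 4.5% in the intervention's favour) describe a rule the plan does not contain. They rest on assumed correlations of 0.95 to 0.5 and a normal approximation. A clarifying sentence would do no harm, but it would only record the natural reading; the test, the sample size and the data collected would stay the same.

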Over three years, we are recruiting a total of 200 adolescent girls (age 13-18) who self-identify as Latina and/or belong to groups considered Latino by the US Census Bureau. Recruitment is done through a variety of approaches including social media advertisements, providing health presentations in classes at local middle and high schools in San Diego County, conducting information sessions at community organization sites, distributing flyers through Latino-serving organizations, and contacting Latina women who have participated in previous studies and given permission to be contacted again to ask if they have family or friends who may be interested in participating.

Randomization, allocation concealment and blinding

Randomization is performed using a random number sequence (generated based on a stratified block randomization procedure) programmed into REDCap clinical trials software.

Randomization is stratified by baseline stage of change according to the TTM (pre-contemplation, contemplation, or preparation) to ensure equal motivational readiness for MVPA adoption across groups. Study group assignment is placed in a sealed envelope based on an order determined by the randomization sequence, with different envelopes designated for each baseline stage of change. Randomization is performed by an interventionist who is not blinded to participant study condition, while staff members completing baseline and follow-up measures remain blinded to condition. Siblings or close friends who enroll together are yoked together into a study arm to minimize contamination between arms; yoked groups are stratified across conditions to ensure equal distribution. After being randomized, participants' Fitbit monitors and app are unblinded to allow for normal use. Participants in the Intervention group then undergo a

goal setting session; those in the control group receive no more direct staff contact until the six-month follow-up visit.

STATISTICAL ANALYSIS

As a preliminary step, the study sample was summarized with respect to baseline socio-demographics and PA rates and compared between groups using t-tests, chi-squared tests and non-parametrics as appropriate. Both participant and parent characteristics at baseline are reported for socio-demographics.

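### Stage of change stratifies the randomisation but is not named in the median regressions, and nothing exempts it from the covariate-dropping rule; any cost is small and in precision

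*Combined protocol and SAP*

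**What the plan says.** The section on randomisation, allocation concealment and blinding states: "Randomization is stratified by baseline stage of change according to the TTM". There are three levels (pre-contemplation, contemplation, preparation). The purpose is "to ensure equal motivational readiness for MVPA adoption across groups", and allocation runs from sealed envelopes, "with different envelopes designated for each baseline stage of change". The same section adds: "Siblings or close friends who enroll together are yoked together into a study arm to minimize contamination between arms".

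The STATISTICAL ANALYSIS section describes quantile regressions with 10,000 bootstrap samples that "regress median min/week MVPA on baseline values, group, and covariates". They are fitted separately for the 7-Day PAR and the accelerometer, with wear time added for the accelerometer. On clustering it says: "we adjusted for clustering by yoked group in each of our models". The remaining covariates are not listed; they are covered by one sentence: "All other covariates were balanced at baseline and tested for significance in the model before being dropped". The section closes with: "All analyses were carried out in R, with significance level set at .05 a priori". Stage of change is not mentioned anywhere in it.

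**The concern.** A factor that decides which envelope is opened belongs in the analysis. Blocking within stage removes between-stage variation from the true sampling error of the group comparison. A model without stage leaves that variation in its residual, so if stage is prognostic the reported standard error is wider than the design warrants.

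The two grounds given for dropping covariates do not answer this. Balance on stage shows that the stratification worked, not that stage can be ignored. A non-significant test is weak evidence at this sample size, and it makes the final model depend on the data. At stake is a little precision in the accelerometer and PAR comparisons, including the six-month accelerometer outcome, which is primary.

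**Working it through.** **Is stage in the final models?** There are two readings. If stage was among the unlisted covariates, it falls under all others and was dropped. If it was not, it was never included. Either way, the final median regressions as described do not contain it.

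**Inputs.** From the documents: N = 200, 1:1 allocation, three strata, α = .05 (taken as two-sided). They give no effect size, SD, power or variance explained by stage, so there is no figure of the plan's own to reproduce. Assumed: an effect of 0.4 SD, and R², the share of residual variance that stage explains once baseline MVPA is in the model. Low R² is plausible, because everyone enrolled is underactive and baseline MVPA is already a term.

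**Step 1, linear approximation with exact balance within strata.**
- SE overstatement = 1/√(1−R²) − 1
- Type I error without stage = 2[1 − Φ(1.96/√(1−R²))]
- δ = 0.4 × √200/2 = 2.828
- Power without stage = Φ((δ − 1.96)/√(1−R²)); with stage = Φ(δ/√(1−R²) − 1.96)

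For R² = .05, √.95 = .9747. The SE is overstated by 1/.9747 − 1 = 2.6%. Type I error is 2[1 − Φ(2.011)] = 4.4%. Power is Φ(.891) = .814 without stage and Φ(.942) = .827 with it.

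| R² | SE overstated | Type I error without stage | Power without / with stage |
|---|---|---|---|
| 0 | 0 | 5.0% | .807 / .807 |
| .01 | 0.5% | 4.9% | .809 / .811 |
| .03 | 1.5% | 4.7% | .811 / .819 |
| .05 | 2.6% | 4.4% | .814 / .827 |
| .10 | 5.4% | 3.9% | .820 / .846 |

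If only 160 are analysed (assumed), the power losses at 1/5/10% are 0.3/1.7/3.4 points.

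**Step 2, simulation closer to the plan.** Median regression with baseline and wear time; bootstrap over yoked clusters (150 samples); 2,125 trials per R². Assumed: 10 yoked pairs with within-pair correlation 0.2, stages split 20/40/40%, blocks of 4 for singles, skewed errors, a constant 0.4 SD shift and no attrition.

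| R² | Mean SE without / with stage | Ratio − 1 | Power without / with stage | Type I error without / with stage |
|---|---|---|---|---|
| 0 | .1303 / .1316 | −1.0% | .880 / .878 | 4.9 / 4.1% |
| .01 | .1304 / .1312 | −0.6% | .876 / .877 | 4.0 / 3.7% |
| .03 | .1309 / .1301 | +0.6% | .866 / .875 | 5.2 / 4.5% |
| .05 | .1306 / .1284 | +1.7% | .870 / .884 | 4.2 / 4.2% |
| .10 | .1316 / .1239 | +6.2% | .874 / .893 | 3.6 / 4.1% |

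Monte Carlo error is 0.5 to 0.7 points for the power differences and about 0.5 for type I error. The SE ratio crosses zero between R² = .01 and .03: 1 + 2 × 0.6/(0.6 + 0.6) = 2%. Up to 5%, type I error shows no clear difference.

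**Step 3, what a non-significant test would show.** At N = 200, a two-degree-of-freedom test at .05 detects a stage effect of 1/2/3/5% with probability .22/.42/.59/.83. A non-significant result therefore points to the low end of the table but does not exclude an effect of 2 to 3%.

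**The case against.** Several points on the other side have force.

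**The threshold is arguably given.** A reader might infer that covariates were dropped by an unstated criterion. The section sets .05 for all analyses, and the natural reading is that this covers the covariate tests. What is missing is the candidate list and the test results, including whether stage was tested.

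**Balance was not the only ground.** The covariates were also tested in the model. That is fair, but Step 3 shows how little a non-significant test settles, and neither ground suits a factor built into the allocation.

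**The gain may be nil.** This stands. In the range of R² that is most plausible, the simulation closer to the plan shows no benefit, and the linear approximation is too favourable there: +0.5% against −0.6% at R² = .01. Comparing mean SEs from two models also does not show directly that either misstates the estimator's true spread. A cruder simulation did make that comparison at R² = .20: mean SE .187 against a true SD of .156 without stage, and .160 against .157 with it. It used kernel standard errors and ignored yoking, so it supports the direction only.

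**Adding stage may change the estimand slightly.** This also stands. Median-regression coefficients need not agree with and without a prognostic covariate, and Step 2 hides this by imposing a constant shift. Illustrative large-sample checks used a 1.5-fold multiplicative effect, a lognormal outcome and no baseline term. They gave group coefficients without/with stage of 20.67/20.66 when stage explained 0.5% and 21.5/20.8 at 6%. With stage strongly prognostic they gave 23.3 without it and between 20.0 and 20.8 with it. The difference is negligible when stage is weak, but the two models should not be presented as estimating exactly the same quantity.

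**Conclusion.** The point stands as a minor one. The plan randomises within stage, does not name stage in its median regressions, and has a drop rule from which stage is not exempt. The size of the consequence rests on R², which is assumed throughout, and on the assumed effect, stage mix and yoking.

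Two stronger readings are not supported. A reader might infer that leaving out the stratifier biases the comparison or inflates false positives. The approximation gives type I error at or below 5%, and the simulation shows no inflation beyond Monte Carlo error. A reader might also extend the point to the Fitbit mixed model. The plan does not say which contrast that model tests, and in complete data a stage main effect leaves a group-by-time contrast unchanged. In one simulated data set the estimate was .4391 with SE .1493 both with and without stage.

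**What to change.** State that stage of change is exempt from the drop rule and is kept as a three-level fixed term in the accelerometer and PAR median regressions at 6 and 12 months, whatever its balance or p-value. Use the level that chose the envelope. Because yoked participants are allocated together, state whose stage applies to them. A stage term in the Fitbit model is optional.

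The analysis section is largely in the past tense. If the models have already been run, keep the primary result and report the stage-adjusted model beside it as a labelled sensitivity analysis, noting that the two group coefficients need not estimate exactly the same quantity. Say also whether stage was among the covariates tested, and with what result.

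The cost is a few sentences of SAP text, two model terms and a re-run. No new data are needed: stage is completed online before the baseline visit and is required to select the envelope. If stage explains nothing, the two terms cost about 1% in standard error and about 0.2 points of power, the latter within Monte Carlo error.

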Participant demographic information is measured via self-report questionnaire at baseline, and includes age, race, and parents' education, income, and marital status.

We also will assess changes in trajectories of daily MVPA measured by the Fitbit Inspire HR. The Fitbit tracker measures physical activity intensity, energy expenditure, bouts of exercise, steps, distance traveled, and flights of stairs at varying resolutions. We will be evaluating the daily active minutes and steps recorded by the Fitbit.

We will also measure technology engagement with the website, Fitbit, texting interactions, and Instagram. Engagement with the *Chicas Fuertes* website measures number of logins and use of specific features, including goal setting, the weekly quiz, and monthly questionnaire completion. Fitbit use is measured as days worn and sync frequency, while texting is based on the percentage of interactive texts the participants responded to. Instagram engagement is measured by the number of views and likes by participants.

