At 12 months, participants in the intervention group were asked to complete a consumer satisfaction measure to assess the acceptability of the intervention. This is modified from our previous studies.

Screening and consenting

Potential participants may contact research staff through Instagram direct message, Facebook, email, or text/call via the study phone number. Interested participants are then called to participate in the telephone screener that includes a description of the study purpose, procedures, risks, benefits, and eligibility requirements. If participant is under the age of 18, research staff first talk with her parent/guardian before screening her to ask basic eligibility questions and to receive parental consent to screen the daughter, then speak to the adolescent to complete screening. If eligible, interested participants are invited to engage in an orientation session via Zoom.

Orientation visit

Prior to the orientation session, participants are instructed to download the Fitbit app and set up an account. They are also provided with an orientation packet via mail, including a Fitbit Inspire HR, a hip-worn accelerometer, and an orientation folder that includes a consent form, assent form, instructions on how to use the Fitbit, and instructions for wearing the accelerometer. The girl's parent/guardian is invited to attend the first half of the orientation via Zoom to review a PowerPoint presentation that outlines the procedures, benefits, and expectations of the study. Following the presentations, the participant and their parent/guardian sign the written informed consent and assent forms, which are collected the following week at the baseline visit. The second half of the orientation is used to set up the Fitbit, including syncing it with a smartphone, connecting it to the study's online Fitabase database, and temporarily blinding the Fitbit monitor and app to prevent feedback from influencing baseline activity. We also review the Fitbit and accelerometer expectations, and schedule the Baseline visit for 7 days after the orientation.

Over the next week, participants wear the Fitbit wrist monitor, and a hip worn GT3X+ accelerometer, with instructions to wear it 12 hours per day for seven days. Before the baseline visit, they also fill out online psychosocial measures, including self-efficacy, stage of change for activity, and social support (see Measures).

Baseline visit

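### The plan lists daily Fitbit activity trajectories and steps as outcomes, but the only Fitbit analysis covers minutes in the measurement weeks and leaves steps out

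*Combined protocol and SAP*

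**What the plan says.** Under Secondary outcomes and covariates, the combined protocol and SAP makes two statements about the Fitbit: "We also will assess changes in trajectories of daily MVPA measured by the Fitbit Inspire HR" and "We will be evaluating the daily active minutes and steps recorded by the Fitbit". It gives these outcomes no rank and no time points. Trial Design and Setting says Fitbits measure activity for the whole study, in contrast to the accelerometer and the PAR, which are used at baseline and follow-up. Both arms have the device for the year, and the Control group section encourages daily wear.

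The Statistical Analysis section has one paragraph on the Fitbit. Its aim is "To understand the group differences in minutes of PA as collected via the Fitbit". Its data are restricted: "we examined data from the weeks corresponding to measurement of PA via the PAR and accelerometer". Its model is given in one sentence: "Using a longitudinal mixed effects model with subject-specific intercepts, we examined group differences adjusting for clustering by yoked pair". Steps are not mentioned in that section.

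The measurement weeks are described elsewhere. At baseline, per Orientation visit: "Over the next week, participants wear the Fitbit wrist monitor, and a hip worn GT3X+ accelerometer". For follow-up, per Follow-up visits: "Prior to the six- and 12-month visits, participants are mailed the accelerometer for one week of wear, similar to baseline".

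**The concern.** The analysis is narrower than the outcome in two ways. A trajectory of daily activity is reduced to the weeks around the visits, and one of the two named metrics has no analysis. The Statistical Analysis section is written in the past tense and gives no reason for the narrowing. A reader therefore cannot tell whether the outcomes were dropped or were analysed and not reported.

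Information is also lost. The intervention changes between visits: the Intervention description says the emphasis shifts between channels over time, and the Text messaging section starts the tailored goal-progress texts in month 2. Between-visit Fitbit data are the only activity record in the plan for those months, and the described analysis does not use them.

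A smaller point is that the model is called longitudinal but its fixed effects are not stated. Whether it tests a group-by-time effect or an average group difference is unclear.

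**Working it through.** The plan gives no figure to reproduce. The check compares the sections and then does a simple coverage count.

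**Outcome against analysis**

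| Feature | Secondary outcomes and covariates | Statistical Analysis |
|---|---|---|
| Activity metric | Daily MVPA; daily active minutes | Minutes of PA |
| Steps | To be evaluated | Not mentioned |
| Time frame | Trajectories, no time points given | PAR and accelerometer weeks |
| Model | Not given | Random-intercept mixed model, fixed effects not stated |

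**Inputs for the coverage count**

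- Measurement weeks: 3 (baseline, before month 6, before month 12). This is inferred from Orientation visit and Follow-up visits; the analysis paragraph does not list the weeks.
- Length of each week: 7 days. This is stated for baseline; follow-up is one week, similar to baseline.
- Fitbit period: the 7-day pre-randomisation week plus 365 days.
- Visits on schedule, with month 6 at day 182 and month 12 at day 365 (assumed).

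**Results**

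- Days used: 3 × 7 = 21.
- Share of the whole period: 21 / (7 + 365) = 21 / 372 = 5.6%. If the baseline week is counted inside the year, 21 / 365 = 5.8%.
- Share after randomisation: 2 × 7 = 14; 14 / 365 = 3.8%.
- Gap from randomisation to the 6-month week: 182 − 7 = 175 days, or 25 weeks.
- Gap from month 6 to the 12-month week: 365 − 182 − 7 = 176 days, about 25 weeks.
- Months contributing data after randomisation: 2 of 12 (months 6 and 12). The 10 unused months include month 1, before tailored texts begin, and months 2 to 5.
- Between-arm changes from baseline that three time points allow: 3 − 1 = 2, at 6 and at 12 months. The change from 6 to 12 months is the difference between these two. Nothing is estimable at dates in between.

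The denominators are calendar days, not days of valid wear. The plan gives no Fitbit variance or wear rate, so any effect on an estimate or its precision cannot be sized.

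**The case against.** The strongest reply is that the outcome is loosely worded. No time points are set, and a longitudinal mixed model at baseline, 6 and 12 months is one way to study change. The unit of analysis is also unstated: with daily records there could be up to 21 values per girl. Matching the Fitbit weeks to the ActiGraph and PAR weeks is sensible in itself. These points stand as far as they go, and the measurement-week model should be kept. But day-level values inside those weeks still say nothing about the roughly 25-week gaps on either side of month 6, and they do not supply an analysis of steps.

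Other measures under the same heading, such as the psychosocial scales and CES-D, have no described analysis at all, so the Fitbit could be seen as one instance of a general gap. That is true. The Fitbit differs because an analysis is described and it falls short of the stated outcome.

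It is also fair to say that the coverage percentages only restate the restriction to measurement weeks, and that no section says the Fitbit outcome is meant to evaluate the phases of the intervention. The percentages are offered only as a description of coverage.

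Finally, an all-weeks analysis has its own weakness, because wear between visits may differ by arm. The Text messaging section gives intervention participants weekly wear-and-sync prompts, while the Randomization section says controls have no direct staff contact until month 6. The contrast may be smaller than this suggests: the adherence section describes automated reminders after four days without syncing and does not say clearly whether controls receive them. Either way, the added analysis can only be supportive.

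**Conclusion.** The concern holds. Followed exactly, the Statistical Analysis section leaves two stated Fitbit outcomes undelivered: the course of daily activity over the year, and steps. The absence of a steps analysis rests on no assumption. The trajectory point rests on the measurement weeks being the only data used, which the plan says. The coverage figures (5.6% of calendar days overall, 3.8% after randomisation) also rest on there being three 7-day weeks with visits on schedule.

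This should be corrected, but it does not threaten the trial's main conclusions. The primary ActiGraph comparison at 6 months and the 12-month maintenance outcome are untouched, and nothing here shows bias in the Fitbit comparison that is described.

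**What to change.** 1. Keep the measurement-week model. State its fixed effects, including a group-by-time term, and run the same model for steps.
2. Add a supplementary longitudinal analysis of all valid-wear Fitbit weeks from baseline to month 12, for active minutes and for steps, with group-by-time and yoked-group clustering.
3. State the valid-week rule used for the Fitbit. The Primary outcome section gives a wear rule for the ActiGraph only. Report wear by arm over time.
4. Present the all-weeks analysis as supportive, and label it as added afterwards if that is the case.
5. If the all-weeks analysis is not done, redefine the outcome as Fitbit minutes at the measurement weeks and disclose the departure from the stated outcome, including that steps were not analysed.

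No new data collection is needed, since Orientation visit has every participant's device linked before randomisation to the "online Fitabase database, and temporarily blinding the Fitbit monitor and app to prevent feedback from influencing baseline activity". The cost is analysis time, including work on the wear rule and on non-wear and sync gaps. How complete the year-long record is cannot be judged from the plan. The redefinition option costs only a disclosure.
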